6.1.2.2. Infections/Infestations

For each phase, TEAEs in the SOC of infections/infestations will be summarized by PT and event onset time (≤ 8 weeks, $8 - \leq 16$ weeks, $16 - \leq 24$ weeks, ≥ 24 weeks). Kaplan-Meier plot of time to first onset of infections/infestations event will also be provided.

6.1.2.3. Neutropenia

For each phase, TEAEs in the PT of neutropenia will be summarized by event onset time (≤ 8 weeks, $8 - \leq 16$ weeks, $16 - \leq 24$ weeks, ≥ 24 weeks). A listing of grade 3 or 4 neutropenia will also be provided.

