3.2.3.2. Daratumumab RP2D Rationale

The RP2D has been selected based on marked M-protein reduction with an acceptable safety profile in doses up to 16 mg/kg, the highest dose of Phase 1. MTD was not reached in Phase 1. The IDMC reviewed the safety data of 2, 4, 8 and 16 mg/kg cohorts and concluded that an acceptable benefit/risk profile was observed in doses up to 16 mg/kg. The majority of the Grade 3 adverse events were neutropenia, which was attributed to lenalidomide. The daratumumab/Len/Dex combination PK-profile was similar to daratumumab alone suggesting Len/Dex does not affect the pharmacokinetic profile of daratumumab.

The rationale of PR2D is also supported by the ongoing single agent daratumumab studies. Clinical pharmacokinetic data have shown the 16 mg/kg dose to be the lowest dose that results in complete target suppression at all time points. This dose and schedule continuously suppressed NK cells throughout dosing. Additionally, the overall response rate (ORR) appeared higher for the 16-mg/kg dose compared with the 8-mg/kg dose, based on early preliminary data from Part 2 of Study GEN501 and from Study MMY2002 (both ongoing) as of a cutoff date of 24 January 2014. In Study GEN501, the ORRs (ie, partial response [PR] or greater) were 11% and 40% for the 8-mg/kg (n=28) and 16-mg/kg (n=15) dose regimens, respectively. For the Study MMY2002, the unconfirmed ORRs for the 8-mg/kg and 16-mg/kg dose regimens were similar to those observed in GEN501. In addition, VGPRs were observed for 7 of 30 subjects treated with the 16-mg/kg dose in those 2 studies. VGPR had not been observed at lower dose levels. These preliminary data support that full target saturation at the 16-mg/kg dose is needed to achieve higher and deeper response rates. In addition, the 16-mg/kg dose and schedule was shown to have an acceptable and manageable safety profile for the approximately 30 subjects for whom preliminary data were available in Studies GEN501 and MMY2002, and no additive toxicity has been observed in the Phase 1 dose escalation when comparing the safety from 16 mg/kg dose cohort with lower dose cohorts.

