6.4. Delaying or Skipping Treatment

After completion of each cycle, initiation of a new cycle should be delayed for at least 1 week if the subject experiences toxicity. A subject whose cycle is delayed should be evaluated weekly for resolution or recovery of the toxicity, and a decision regarding further delay or initiation of

Key: CrCl = creatinine clearance.

Estimated by CrCl as calculated by the Cockcroft-Gault, Diet in Renal Disease (MDRD), or Chronic Kidney Disease Epidemiology Collaboration (CKD-EPI) formulas formula (Attachment 7).

the next cycle should be made. However, the start of a new cycle after more than a 3-week delay (with all study therapy withheld) may occur only if there is clear clinical benefit and only after approval by the sponsor.

Refer to Section 6.6.1 for details on management of infusion-related reactions. **ONLY if any of the following criteria below are met, and the event cannot be ascribed to lenalidomide, the daratumumab infusion must be held to allow for recovery from toxicity**. The following parameters must be met on the first day of a new cycle (after Cycle 1):

- Platelet count $\geq 50 \times 10^9/L$
- Febrile neutropenia of any grade
- Neutropenia with infection, of any grade
- Hemoglobin $\geq 8.0 \text{ g/dL}$ ($\geq 4.96 \text{ mmol/L}$) (prior red blood cell transfusion or recombinant human erythropoietin use is allowed)
- ANC $\ge 0.75 \times 10^9 / L$
- Nonhematologic toxicity of Grade 3 or higher must have recovered to baseline or Grade 1 or less unless otherwise specified

A subject whose cycle is delayed should be evaluated at least weekly for resolution of the toxicity. For severe hematologic toxicity (Grade 3 or higher), a complete blood count may be repeated more frequently as necessary until the requirements for reinitiating treatment are met.

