6. SAFETY

For all treated subjects in Phase 1, and for safety population in Phase 2, the safety profiles of daratumumab or combination with Len/Dex will be evaluated by the incidence of adverse events (AEs), death, laboratory results, vital signs, physical examination findings, and ECG results.

Safety evaluations will be made by treatment actually received. The severity of AEs and the toxicity of laboratory parameters will be assessed using NCI CTC version 4.03. Adverse events are coded using MedDRA version 17.0.

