6.1.1. Treatment Emergent Adverse Events

The following summaries will be provided for all TEAEs:

- An overview of TEAE will be provided, including the incidence of TEAE, serious TEAE, maximal severity of TEAE, treatment discontinuation due to TEAE, TEAE leading to treatment interruption, and death due to TEAE.
- An overview of TEAE by subgroups specified in Section 2.4
- Separate listings for each category above.

In addition, the following summaries will be generated:

- TEAEs by system organ class (SOC) and preferred term (PT)
- Most common (at least 5%) TEAEs by system organ class (SOC) and preferred term (PT)
- TEAEs by SOC, PT, and grade 3 or 4.
- TEAEs by SOC, PT, and worst toxicity grade
- TEAEs by SOC, PT, and relationship to study medication
- Most common (at least 10%) TEAEs by system organ class (SOC), preferred term (PT), and grade 3 or 4.
- TEAEs by SOC, PT, and grade 3/4 by subgroups specified in Section 2.4
- Serious TEAEs by SOC and PT
- Serious TEAEs by SOC, PT, and worst toxicity grade
- Serious TEAEs by SOC, PT, and relationship to study medication
- Most common (at least 1%) serious TEAEs by system organ class (SOC) and preferred term (PT)
- Grade 3 or 4 TEAEs by SOC and PT
- Grade 3 or 4 TEAEs by SOC, PT, and relationship to study drug

The following summaries for TEAEs leading to treatment modifications will be provided:

- TEAEs leading to infusion interrupted by PT, and relationship to study drug
- TEAEs leading to infusion prolonged by PT, and relationship to study drug.
- TEAE leading to hospitalization or prolonged hospitalization by SOC and PT.
- Treatment discontinuation due to TEAEs by PT and relationship to study drug
- Study discontinuation due to TEAEs by PT and relationship to study drug
- Death due to TEAEs by PT and relationship to study drug.

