6.1.2. Adverse Events of Clinical Interest

6.1.2.1. Infusion Related Reactions

For each phase, the infusion related reactions (IRRs) will be clinically reviewed and identified. The incidence of IRRs will be presented by SOC, PT, and toxicity grade (any grade and grade 3 or 4). The incidence of IRRs will also be presented by type of pre-infusion steroids.

The time to onset of infusion related reaction will be summarized.

All infusion related reactions will be also listed.

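### The neutropenia onset-time summary in SAP 6.1.2.3 counts one preferred term only, so no planned output gives a pooled incidence or onset time for neutropenia-type events

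*SAP*

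**What the plan says.** SAP 6.1.2 sets three topics apart under the heading "Adverse Events of Clinical Interest": infusion-related reactions, infections and neutropenia. For neutropenia, in each phase, "TEAEs in the PT of neutropenia will be summarized by event onset time", in four onset periods with cut points at 8, 16 and 24 weeks. The section then adds: "A listing of grade 3 or 4 neutropenia will also be provided". It does not say which terms count as neutropenia for that listing.

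The other two topics are defined more broadly. Infusion-related reactions are identified by clinical review. For infections, "TEAEs in the SOC of infections/infestations will be summarized by PT and event onset time", so a whole system organ class (SOC) is taken in and then broken down.

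On coding, SAP section 6 says only that "Adverse events are coded using MedDRA version 17.0". Neither document names a grouped term, a standardised query or a list of related PTs for neutropenia.

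The protocol explains why the topic was singled out. Section 3.2.3.2 reports from Phase 1: "The majority of the Grade 3 adverse events were neutropenia, which was attributed to lenalidomide". Section 6.4 lists febrile neutropenia and "Neutropenia with infection, of any grade" as items apart from the neutrophil-count threshold, and section 6.5 separates asymptomatic grade 4 neutropenia from neutropenic fever.

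**The concern.** A fall in neutrophils can reach the database in several forms: as a diagnosis of neutropenia, as a febrile complication, or as an abnormal count. Protocol 12.4.1 counts laboratory abnormalities as adverse events, and Protocol 11.11 codes from the investigator's verbatim term. A summary built on one PT counts only the forms that code to that PT. A subject whose only record codes elsewhere is treated as having had no event.

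Safety is the primary objective, neutropenia was the most frequent Grade 3 event in Phase 1, and SAP section 3 says the data cut is meant to support a licence application. A reader would take the neutropenia section as the place to find how often and how early neutropenia occurred. If related terms are in use, its answer would be too low and, for some episodes, too late.

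**Working it through.** The SAP states no figure for this item, so there is none to reproduce. The check is mainly textual, with one line of arithmetic for scale.

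**1. What the rule counts.** Membership of the onset-time summary requires the PT neutropenia (SAP 6.1.2.3). An event under any other PT cannot enter.

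**2. Whether another output supplies the pooled result.**

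- *SAP 6.1.1* tabulates all treatment-emergent events by SOC and PT, with further tables by worst grade, grade 3 or 4, seriousness and relationship. Related terms therefore appear as separate rows. Rows cannot be added to give a subject count, because one subject may appear in several. With row counts *a*, *b* and *c* among *N* subjects, the pooled count can lie anywhere from max(*a*, *b*, *c*) to min(*N*, *a* + *b* + *c*). These tables also carry no onset time.
- *SAP 6.3* gives worst laboratory grade, change from baseline and grade shifts for applicable parameters. Neutrophils are not named, but Protocol 9.2.2.2 collects a white cell count with differential at each visit, so they should be covered. No time to first grade 3 or 4 value is specified.
- *SAP 2.6.13* links consecutive records only when they share a PT. An episode recorded first under another term and later as neutropenia takes the later onset date, and may move to a later onset period. An episode that becomes febrile neutropenia under its own PT is not joined to the earlier record.

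No planned output therefore gives a pooled subject-level incidence or an onset pattern for these events.

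**3. Scale.** Inputs: *N* of about 30 in Phase 2 (SAP 1.4), and *k*, the number of subjects whose only neutropenia-type event is coded to another PT. The documents do not give *k*; 0 to 5 is an assumption. With all *N* subjects as denominator, the shortfall in percentage points is 100 × *k* / *N*.

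| *k* | Calculation | Shortfall (points) |
|---|---|---|
| 0 | 100 × 0 / 30 | 0 |
| 1 | 100 × 1 / 30 | 3.3 |
| 2 | 100 × 2 / 30 | 6.7 |
| 3 | 100 × 3 / 30 | 10.0 |
| 5 | 100 × 5 / 30 | 16.7 |

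A subject with events under both terms is still counted, so such subjects add nothing to *k*, although their onset time may be wrong.

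**The case against.** The strongest reply is that nothing leaves the safety report. The primary endpoint is the incidence of all adverse events (Protocol 9.3), and SAP 6.1.1 excludes no PT. Febrile neutropenia under its own term would have its own row there, and would appear in the serious-event tables if serious. Laboratory grading does not depend on how a site words an event. Protocol 12.6.1 asks for diagnoses in preference to separate signs and symptoms, which should reduce variation in wording. Showing febrile neutropenia apart from uncomplicated neutropenia is also a reasonable choice in a descriptive study with no hypothesis test.

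Most of this stands. A reader might infer that the main toxicity analysis omits the most serious neutropenic events. It does not: SAP 6.1.2.3 is a supplementary breakdown. A reader might also infer that the grade 3/4 listing is confined to the single PT. The PT restriction is in the sentence before the listing, so the listing's scope is undefined and cannot be called restricted.

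The protocol items on febrile neutropenia and on neutropenia with infection are criteria for holding an infusion. They show that the protocol distinguishes these events clinically, but not how they are coded. Nothing shows that neutropenia with infection would be coded away from neutropenia, and its infection component would fall in the infections summary.

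The reply does not answer the gap found in step 2. Separate PT rows and a pooled group can sit in the same table, so the preference for separate rows is no reason to leave out the pooled one.

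**Conclusion.** The point holds as a limited one. The neutropenia onset-time summary follows a stated rule that misses any subject whose only neutropenia-type event is coded to another PT. It is narrower than the rules for the other two events of clinical interest, and the SAP gives no reason for this. The loss is a combined incidence and an onset pattern; the individual events remain reported.

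The size cannot be determined from the documents, which give no count or rate for neutropenia or any related term. Under the assumption of 0 to 5 affected subjects among about 30, the reported Phase 2 incidence would be 0 to 16.7 points too low, at 3.3 points per subject. If the coders bring all such events under one PT, the loss is nil. The documents do not support a more specific percentage, nor any claim that the primary endpoint is affected. This is a worthwhile low-cost improvement, not a flaw that threatens the trial's conclusions.

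**What to change.** In SAP 6.1.2.3:

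- Define neutropenia as a pre-specified group of PTs. Candidates are neutropenia, febrile neutropenia and decreased neutrophil count, with the list fixed against the dictionary version in use.
- Report, by phase and onset period, the number and percentage of subjects with any term in the group. Keep the individual PT rows beneath it so that febrile events stay visible.
- Take onset as the earliest record under any term in the group. This removes the effect of linking within a single PT.
- State that the grade 3/4 listing uses the same list.
- Add one table of time to first grade 3 or 4 neutrophil count from the differential already collected. Label it as time to first observed value, because the scheduled visits become less frequent in later cycles (Protocol Table 2).

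The cost is a term list and one extra table. No new data, sample size or design change is needed, and no treatment rule is affected.

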6.2. Deaths

For each phase, number of patients who died during the study and the primary cause of death will be summarized. In addition, all deaths within 30 days of last study drug will be summarized.

A listing will be generated for all patients who died during the study.

6.3. Clinical Laboratory Tests

For each phase, treatment-emergent worsening worst toxicity grade during treatment will be tabulated for applicable laboratory parameters. Descriptive statistics for values and changes from baseline for these laboratory parameters will be provided. In addition, shifts from baseline toxicity grade to worst toxicity grade during treatment will be generated.

Shifts from baseline during treatment will be summarized for natural killer cells also.

6.4. Vital Signs and Physical Examination Findings

For each phase, descriptive statistics will be provided for values and changes from baseline over time for vital signs, together with minimal, maximal, last value on study, and their changes from baseline.

Post baseline physical examination findings were collected as AEs, and therefore will not be summarized.

6.5. Electrocardiogram

Frequencies of overall interpretation of ECG results (normal, abnormal and clinically significant, abnormal and not clinically significant) over time will be provided.

All the ECG results and the change from baseline overtime will be listed. QTcB/QTcF intervals and the change from baseline overtime will be summarized for each phase using the QT evaluable analysis set.

6.6. Other Safety Parameters

6.6.1. ECOG Performance Status

For each phase, frequencies of ECOG performance status (0, 1, 2, >2) over time will be summarized. Shifts from baseline ECOG performance status to the best scoring during treatment will be generated. All ECOG performance status for each patient will be listed.

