Phase 2: Biomarker assessments may include further understanding the MOA (ADCC/CDC/ADCP) of daratumumab in combination with lenalidomide and dexamethasone, immunophenotyping, evaluation of complement proteins, soluble CD38, and multiple myeloma cell profiling (including CD38/CD46/CD55/CD59 expression). In addition, exploratory proteomics and SNP analysis may be performed. Biomarker analyses are dependent upon the availability of appropriate biomarker assays and may be deferred or not performed if during or at the end of the study it becomes clear that the analysis will have no scientific value, or if there are not enough samples or not enough responders to allow for adequate biomarker evaluation. In the event the study is terminated early or shows poor clinical efficacy, completion of biomarker assessments is based on justification and intended utility of the data.

PHARMACOGENOMIC (DNA) EVALUATIONS

A pharmacogenomic blood sample will be collected to allow for pharmacogenomic research, as necessary (where local regulations permit). Subject participation in the pharmacogenomic research is optional.

SAFETY EVALUATIONS

Safety variables are the incidence of AEs, physical examination findings, electrocardiogram results, vital sign measurements, ECOG performance status, laboratory test results, and immunogenicity assessments.

Dose-limiting Toxicity:

Dose-limiting toxicities are defined as any of the following events that occur during the first treatment cycle (28 days):

- Nonhematologic toxicity considered to be a serious adverse event (SAE) of grade 3 or higher and related to daratumumab with the exception of:
 - Any nonhematologic reaction of grade 3 or higher that has an onset after the start of infusion on an infusion day, responds to symptomatic therapy, and resolves within 6 hours from onset
- Adverse reactions that prevent the infusion from being resumed regardless of the length of the reaction
- Hematologic toxicity, considered related to daratumumab, defined as
 - Thrombocytopenia (platelet count $< 20,000 \text{ cells/}\mu\text{L}$)
 - Asymptomatic grade 4 neutropenia for more than 3 days
 - Neutropenic fever (defined as grade 3 or 4 neutropenia and temperature > 38.5°C) for more than 3 days
- Inability to receive the Day 1 infusion of Cycle 2 because of any toxicity related to daratumumab

STATISTICAL METHODS

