11.11. Safety Analyses

The verbatim terms used in the CRF by investigators to identify adverse events will be coded using the Medical Dictionary for Regulatory Activities (MedDRA). All reported adverse events with onset during the treatment phase (ie, treatment-emergent adverse events, and adverse events that have worsened since baseline) will be included in the analysis.

The number and percentage of subjects with treatment-emergent AEs will be summarized according to intensity by using the CTCAE v4.0, drug relationship, and outcome. Laboratory data will be summarized and descriptive statistics will be calculated. Changes in vital sign measurements, physical examination findings, and ECOG performance status will be summarized. Safety laboratory variables will be presented in figures (values versus time) and summarized by value and change from baseline (both absolute and relative).

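### The only baseline-paired ECOG table in the safety section uses the best on-treatment score, so it misses most declines and overstates improvement

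*SAP*

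**What the plan says.** Both documents treat ECOG as safety data. The Safety Evaluations paragraph of the Protocol Synopsis lists it among the safety variables ("vital sign measurements, ECOG performance status, laboratory test results, and immunogenicity assessments"). The SAP places it under "6.6. Other Safety Parameters". Protocol 11.11 sets the requirement: "Changes in vital sign measurements, physical examination findings, and ECOG performance status will be summarized". It does not mention a best score.

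SAP 6.6.1 plans three outputs:
- by visit: "frequencies of ECOG performance status (0, 1, 2, >2) over time will be summarized";
- paired with baseline: "Shifts from baseline ECOG performance status to the best scoring during treatment will be generated";
- individual data: "All ECOG performance status for each patient will be listed".

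No shift to the worst or last score is planned, and no reason is given for choosing the best. Elsewhere in SAP Section 6, laboratory data are handled in the direction of harm ("shifts from baseline toxicity grade to worst toxicity grade during treatment will be generated"). Vital signs are shown in both directions and at the end ("together with minimal, maximal, last value on study, and their changes from baseline").

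**The concern.** A safety shift table should let a reader see how many subjects got worse and by how much. Taking the best of repeated scores works against that in two ways. A real decline disappears if the subject was ever scored at or above the starting level, and most subjects who decline after a stable period will have been. In addition, the more often a stable subject is scored, the more likely it is that one chance good score becomes his or her entry in the table.

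The primary objective is the safety profile, and SAP Section 3 says that the data cut is meant to support a licence application. There is no control arm against which to judge an apparent improvement. A reader who takes this table as the ECOG change summary promised in Protocol 11.11 would get too favourable a picture.

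**Working it through.** The plan gives no figure for ECOG, so there is nothing to reproduce. The check follows the rule itself and then illustrates its size.

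**Inputs from the documents**
- Entry ECOG is 0, 1 or 2 in both phases (Protocol 4.2).
- After baseline, ECOG is scheduled on Day 1 of each cycle from Cycle 2 and at the End of Trial (EOT) visit (Protocol Tables 1 and 2). Cycles last 28 days.
- At the primary analysis every subject has had at least 12 months of study drug or has discontinued (SAP Section 1). Twelve months is 365.25/28 = 13.0 cycles. A subject treated throughout therefore has about k = 12 cycle-start scores (Cycles 2 to 13). A subject treated through Cycle 6 has k = 5 (Cycles 2 to 6).

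**Assumptions not in the documents**
- At each visit there is a probability q of a recorded score one grade better than the true state, and the same q of one grade worse. q is varied from 0.02 to 0.15.
- Scores are independent between visits.
- For apparent improvement, baseline ECOG is 1 or 2, because a subject at 0 cannot improve.

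**Step 1: decline.** Lower ECOG is better, so the best score is the minimum. The minimum exceeds baseline only if all k scores do. A subject with baseline 1 and scores 1, 2, 2 is tabulated as 1 to 1. Now suppose that 30% of subjects have a sustained one-grade decline starting at visit 2 or later of 12. The proportions shown as worsened, from a simulation of 200,000 subjects, are:

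| q | Best score | Worst score | Last score |
|---|---|---|---|
| 0 | 0% | 30% | 30% |
| 0.05 | 0.1% | 62% | 32% |
| 0.10 | 0.1% | 80% | 34% |

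The first row needs no assumption about scoring error. It needs only that the first on-treatment score is no worse than baseline.

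**Step 2: chance improvement.** With no true change, P(best score shows improvement) = 1 − (1 − q)^k.

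| q | k = 5 | k = 12 |
|---|---|---|
| 0.02 | 10% | 22% |
| 0.05 | 23% | 46% |
| 0.10 | 41% | 72% |
| 0.15 | 56% | 86% |

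For example, 1 − 0.98^12 = 0.215 and 1 − 0.85^12 = 0.858. A single last score would show improvement with probability q only.

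**Step 3: the worst score has the mirror-image problem.** By symmetry, the same formula gives the chance that a stable subject looks worsened in a worst-score table: 46% at q = 0.05 and k = 12. The excess of the worst-score column over 30% in Step 1 is this effect. The last-score column stays close to 30%.

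**Step 4: what the other two outputs show.** Because entry is limited to 0 to 2, any count in the >2 category is a decline in an eligible subject. Within 0 to 2 the frequencies cannot be traced to individuals. If one subject goes from 0 to 1 and another from 1 to 0, the counts do not change. A subject who falls from 1 to 2 looks the same as one who entered at 2. The listing contains every sequence, but the reader must do the summarizing.

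**The case against.** The strongest reply is that the shift table does not stand alone. SAP 6.6.1 also plans by-visit frequencies and a complete listing. Enrolment is only 42 to 58 subjects, so the listing can be read in full. A marked decline, such as 1, 1, 3, would appear in the >2 category. Withdrawals with reasons, discontinuations due to adverse events, and deaths are reported separately. All of this stands. A reader might infer that the safety section as a whole hides deterioration. The documents do not support that; the defect is confined to one table.

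A reader might also infer that the frequencies fail because subjects who decline leave and take their last score with them. That goes too far as well. ECOG is scheduled at the EOT visit, and SAP 2.1 presents data over time by the time points recorded in the case report form. Leaving treatment therefore does not automatically remove the final score.

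Two further replies have some force. First, the SAP has no uniform worst-value rule for safety data, so the laboratory convention does not by itself make a best-score ECOG table an error. That is correct; the case rests on what the best-score rule can and cannot show. Second, the error rates are assumed and independence is generous. That is why a range is given. Positive correlation between visits would shrink the chance effect without reversing it.

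What the replies do not answer is that Protocol 11.11 asks for a summary of changes. The only paired summary planned runs in the favourable direction.

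**Conclusion.** The point holds for the shift table. It cannot register a decline in any subject with one on-treatment score equal to or better than baseline. It also overstates improvement in subjects starting at ECOG 1 or 2. The first conclusion follows from the rule alone. The size of the second, 22% to 86% over 12 visits and 10% to 56% over 5, depends on the assumed q, the number of scores and their independence, and should be read as an illustration.

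The consequence is limited. The output is descriptive, SAP 5.1.1 plans no formal test, and no decision rule uses the table. The primary endpoint, incidence of adverse events, is unaffected. A reader might infer that the plan presents ECOG improvement as a treatment benefit; the SAP nowhere says so.

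**What to change.** In SAP 6.6.1, plan shifts from baseline to the worst and to the last on-treatment ECOG score, and state that the EOT score counts. Keep the best-score shift only if it is labelled as such and shown beside the other two. Keep the by-visit frequencies and the listing unchanged.

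Replacing best with worst alone is not enough, because that table would lean toward worsening by chance. The last score has no such selection and should be shown with it. The cost is one revised SAP sentence and one or two extra tables; no new data are needed.
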